We will work with the each health system to gather data from EHR. For women in Groups 1 and 2, we will confirm whether any received a clinic-based cervical cancer screening test during Year 2. For women in Group 1 who tested positive for a high-risk HPV type based on their self-test, we will also confirm: a) any follow-up appointment attended; b) any follow-up care received (e.g., Pap test, colposcopy, etc.); and c) any cervical abnormalities (precancerous and cancerous) found during this follow-up. During this process involving EHRs, members of the project team will not have access to any identifying information (including contact information) of the patients. All communication between the project team and clinics about participants will involve only ID numbers. This information will be entered into a database by clinic staff (see Appendix).

Patient Satisfaction Survey

All women who were sent an HPV self-test during Year 2 (i.e., Group 1) will be sent a patient satisfaction survey about HPV self-testing (see Appendix) and an introductory letter about the survey (see Appendix). The survey will be sent to both self-test returners and non-returners. The clinics will mail all of the surveys to participants, with each survey containing the participant's unique ID number. Members of the project team will not have access to any identifying information (including contact information) of the patients. All communication between the project team and clinics about participants will involve only ID numbers.

The survey will examine women's decisions/experiences with their self-test and PN (if applicable), as this information will be valuable in evaluating the intervention. The survey will assess reasons for returning or not returning the self-test, satisfaction with the self-test (appearance, usability, etc.) and its instructions (appearance, readability, etc.). For women who received PN, the survey will assess their satisfaction with PN. Women will be provided with a postage-paid return envelope, and survey return will be considered consent. Women will be sent a \$25 gift card for returning the survey (see Appendix for letter that will be sent with the gift card).

Year 3 Randomized Trial Activities

Group 1: Bundling

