Group 1 clinics/health systems will continue with the Sustainability phase, as described above during Year 5. Group 2 clinics/health systems will also enter the Sustainability phase, as described above, during Year 5. In this phase, 100 women across Group 1 health systems and 100 women across Group 2 health systems who remain unscreened/underscreened will be randomly sampled from the sampling frame and sent an HPV self-test.

Data Collection for Year 5

Data collection activities (Medical Record Review and Patient Satisfaction Survey) will be identical to those described for Year 3.

Statistical Methods: Analyses and Evaluation

We will conduct analyses/evaluation of each outcome type recommended for implementation research:³² implementation, service, and client outcomes.

Aim 1 (Service Outcomes)

Service outcomes will include intervention effectiveness, equitableness, and safety (Table 1). We hypothesize the intervention will increase cervical cancer screening and that PN will increase HPV self-test return among women who do not initially return their self-test (Hypothesis 1a). We think PN will increase HPV self-test return among these initial non-returners given PN's positive effect on health outcomes in past studies.²⁶⁻²⁹ Lastly, we hypothesize the increase in screening will be similar across patient characteristics (i.e., equitableness)(Hypothesis 1b).

Table 1. Service Outcomes and Data Sources

Outcome	Measure	Level	Data Source
Effectiveness	Cervical cancer screening	Patient-level	HPV self-test data and medical records
Equitableness	Demographic and health-related characteristics	Patient-level	Medical records
Safety	Reported issues in using an HPV self-test	Patient-level	Patient satisfaction surveys

Measures

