The patient-level effectiveness outcome and primary outcome for our project will be whether or not women get "screened" during the project. There are three ways a woman can be considered "screened." The first is to return their HPV self-test and test negative for high-risk HPV types. The second is to return their HPV self-test, test positive for high-risk HPV types, and then attend a follow-up appointment at their health system. We are requiring these women to attend a follow-up appointment to be considered "screened" given their HPV infection. The third way is to receive a clinic-based screening test (e.g., Pap test), regardless of HPV self-test return status. This will most likely apply to women in Group 2 health systems during the Usual Care Continued phase, but past studies have shown that some women will get a Pap test after receiving an HPV self-test in the mail (without using the self-test).⁴² All women not meeting one of these three criteria will be considered "unscreened." To determine this outcome, we will examine HPV self-test return status, HPV testing results, and EHR data (follow-up appointment attendance, Pap testing, etc.) for each sampled woman.

Among women who return their HPV self-test, we will examine the timing of device return and categorize each as returned within two weeks of distribution (i.e., prior to any PN) or after two weeks of distribution (i.e., following PN). We will also examine HPV testing results (positive or negative for high-risk HPV types) and collect data from EHR on the number of normal and abnormal clinic-based cervical cancer screening tests received by each woman and any cervical abnormalities found (i.e., low-grade squamous intraepithelial lesion, etc.).

To assess if the intervention is equitable (Figure 4), we will examine patient characteristics via data from HER (e.g., age and when their most recent clinic-based cervical cancer screening test prior to project entry occurred [if

ever]). Lastly, to assess safety, we will examine data from the patient satisfaction survey to see if women report any issues about using their HPV self-test. We do not anticipate such reports to be common, as HPV self-test devices have been used safely and easily by women in several research studies.⁶⁻¹⁵

Sample Size

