We will conduct several secondary analyses for Aim 1. First, we will examine the proportion of HPV self-test returners who returned their self-test following receipt of PN. Results will provide valuable data on the added benefit of PN on HPV self-test return. Second, we will use GLMMs with a logit link to examine potential differences in the proportion of women screened across project years within each treatment group (i.e., comparing Years 2, 3, 4, and 5 for Group 1). Results will determine how screening rates changed over time, which will be key in assessing whether the intervention was maintained during the Bundling and Sustainability phases. Third, to assess if the intervention was equitable, we will use GLMMs with a logit link to examine if patient characteristics are associated with women being categorized as "screened". Fourth, to assess safety, we will descriptively examine women's reports of any issues experienced when using their HPV self-test. Lastly, we will descriptively examine the prevalence of high-risk HPV infection, abnormal clinic-based cervical cancer screening tests, and cervical abnormalities among women.

Aim 2 (Implementation Outcomes)

Implementation outcomes will examine the fidelity, sustainability, and cost-effectiveness of the intervention. We hypothesize that the intervention will be implemented with high fidelity and sustained by the clinics/health systems (Hypothesis 2a). We also hypothesize that the intervention will be a cost-effective strategy for increasing cervical cancer screening (Hypothesis 2b).

Fidelity

We will use several strategies to ensure and examine fidelity (i.e., the degree to which the intervention is conducted according to protocol). At the patient-level, we will develop an electronic tracking system to track all mailings (e.g., self-test distribution) and other data collection activities. At the provider level, we will conduct the provider education sessions using a standardized PowerPoint presentation. Data during the sessions will be collected using a checklist (for project team use only) that includes key observations related to fidelity (e.g. the presence of participants during entire session).

Sustainability

We will examine the screening rates during the Sustainability phase(s) for both Groups 1 and 2 to determine sustainability.

Cost-effectiveness

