We believe these education sessions will present minimal risk to participants. We do not anticipate harm to study participants. We do not anticipate any psychosocial harm, economic harm, legal jeopardy, or other side effects for these individuals. There is the small possibility that some participants may find some of the session topics or survey items embarrassing or worrisome. However, education sessions and surveys of this type are routinely conducted, with no ill effects to participants.

Randomized Controlled Trial

We believe the RCT will also present minimal risk to participants. We do not anticipate physical harm to study participants. We also do not anticipate any psychosocial harm, economic harm, legal jeopardy, or other side effects to participants. HPV self-tests have been used in numerous studies without causing physical or psychosocial harm,⁶⁻¹⁵ and most women report low levels of discomfort and anxiety when using HPV self-tests. Instructions describing how to use the HPV self-test will be provided to all women along with their self-test device. Women will also be provided with contact information in case they have any questions or problems with the HPV self-test. There is the small possibility that some participants may experience anxiety after being notified of their HPV self-test results. Such effects are not common among women who receive negative HPV results, but could occur among women with positive results. In order to minimize this risk, women will be provided with contact information for the clinic and PN when they receive their HPV self-test results. Further, a PN will contact all women who test positive for a high-risk HPV type.

It is also not anticipated that the Patient Satisfaction Survey will cause any psychosocial harm, economic harm, legal jeopardy, or other side effects. Some women may find some of the survey questions embarrassing or

worrisome since this study focuses on HPV and cervical cancer prevention. However, surveys of this type are routinely conducted, with no ill effects to participants. Because all study surveys will be sent and returned via mail and completed by women in their homes with the option to skip any question they do not wish to answer, this is a minimal risk. We asked similar survey questions in our pilot study without any resulting problems.²⁴

Protection Against Risk

Provider Education Sessions

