All participants will provide informed consent before focus groups. The autonomy of participants will be protected by informing all participants of the purpose of the study and allowing them to opt out of participation without repercussion. Participants will be able to withdraw from the study at any time, and they will be able to refuse to answer any survey question.

Several precautions will be taken to avoid any breach of confidentiality. We will use identification numbers instead of the names of participants (or any other personal identifiers) on all session forms and in any database containing study data. The numbers and names will be linked in a separate study tracking database list that will be accessible only to the study team. All databases will be password protected behind the OSU firewall. All completed session forms (e.g., surveys) will be stored in locked file cabinets. Only members of the study team will have access to these hard copy documents.

We will use REDCap (Research Electronic Data Capture) to collect data online, as needed (e.g., provider education surveys). REDCap is a software toolset and workflow methodology for electronic collection and management of clinical and research data. The Ohio State Research Information Technology Electronic Data Capture will be used as a central location for data processing and management. REDCap provides a secure, web-based application that provides an intuitive data manipulation interface, custom reporting capabilities, audit trail functionality, real-time data monitoring/querying of participant records, and variations of data exporting/importing. REDCap is hosted by OSUWMC IT in the Ackerman Datacenter ([name]).

Randomized Controlled Trial

Every means will be taken to minimize the risk associated with participating in the RCT. The autonomy of participants will be protected by informing all participants of the purpose of the study and allowing them to opt out of participation without repercussion (i.e., women will not have to use the HPV self-test device or survey sent to them). For both the HPV self-test and Patient Satisfaction Survey, return of the device (or survey) will be considered consent. Participants will be able to withdraw from the study at any time, and they will be able to refuse to answer any survey question. Participants will be provided with contact information in case they have any questions or concerns or experience any negative outcomes.

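### The descriptive safety outcome draws only on the voluntary mailed satisfaction survey; no route brings in device problems reported to navigators or through the contact information given to women

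*Combined protocol and SAP*

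**What the plan says.** Table 1 under Aim 1 (Service Outcomes) lists safety as a patient-level outcome, measured as "Reported issues in using an HPV self-test", and its data-source column names patient satisfaction surveys only. The Measures section repeats this: "we will examine data from the patient satisfaction survey to see if women report any issues about using their HPV self-test". Secondary Analyses adds a descriptive look at women's "reports of any issues experienced when using their HPV self-test", without naming another source or a denominator.

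The survey is described under Data Collection for Year 2. It is mailed by the clinics, a $25 gift card follows its return, and "survey return will be considered consent". It reaches everyone sent a kit: "The survey will be sent to both self-test returners and non-returners". Aim 3 (Patient-Level) expects about 80% to send it back.

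Elsewhere the protocol opens other routes. Under Potential Risks and Benefits, for the randomized trial: "Women will also be provided with contact information in case they have any questions or problems with the HPV self-test". Under Protection Against Risk: "Participants will be provided with contact information in case they have any questions or concerns or experience any negative outcomes". The two patient navigation sections have clinic-employed navigators try to contact every woman who has not returned her kit at two weeks, and every woman who tests positive for high-risk HPV. Women whose kit has already come back by the time of the call are asked whether they had questions.

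**The concern.** The plan gives women a way to report problems, and it has navigators speaking with many of them about using the device, but the safety outcome does not draw on either. A woman who reports a device problem to her navigator and never mails the survey is not in the outcome, although clinic staff know of the problem.

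The data flow makes this unlikely to correct itself. Study team members have no direct contact with participants, and communication with the clinics about participants uses ID numbers only. A problem heard at a clinic reaches the analysts only if someone is asked to send it. In the Sustainability phase the team steps back and is consulted only on issues the clinics cannot settle, so a problem the clinic resolves would stay there.

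At stake is the completeness of the safety statement. The plan expects such reports to be uncommon, so each omitted one carries weight. Leaving out known problems can only reduce the count.

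**Working it through.** The plan states no figure for safety, so there is none to reproduce. The first step is a reading of the text and the second is a count of the gap.

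**Where a device problem could surface, and whether the plan uses it**

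- Satisfaction survey: named as the safety source in Table 1 and in Measures.
- Contact information for problems or negative outcomes: provided, but no recording, forwarding or counting is described.
- Navigator contacts: navigators are trained to complete project forms, but nothing links those forms to safety.
- Medical record review: collects clinic-based screening tests, follow-up visits, follow-up care and cervical abnormalities, not device problems.

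**Women sent a kit, Years 2-5**

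- Group 1: 600 + 100 + 100 + 100 = 900.
- Group 2: 100 + 100 + 100 = 300 (its 600 women in Year 2 continue usual care and get no kit).
- Total: 900 + 300 = 1200. This agrees with the stated 1800, since 1800 − 600 = 1200.
- Kits sent in a Sustainability phase: 100 (Year 4, Group 1) + 200 (Year 5, both groups) = 300.

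**Women with no survey**

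- At the plan's 80% return: 0.20 × 1200 = 240.
- Over an assumed return of 60% to 90%: 0.40 × 1200 = 480 down to 0.10 × 1200 = 120.

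**Users with no survey**

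The outcome concerns use of the device, so users are the relevant group. The plan gives no expected kit use. I assume 20% to 40% of 1200, and that users return surveys at the same 80%. The last two columns give the upper 95% bound on the true problem rate if no problem is reported, 1 − 0.05^(1/n), with n first the users who answered and then all users.

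| Assumed use | Users | With survey | Without | Bound, survey users | Bound, all users |
|---|---|---|---|---|---|
| 20% | 240 | 192 | 48 | 1.55% | 1.24% |
| 30% | 360 | 288 | 72 | 1.03% | 0.83% |
| 40% | 480 | 384 | 96 | 0.78% | 0.62% |

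At 30% use, full survey response would tighten the bound by only 1.03 − 0.83 = 0.20 percentage points. The gap is mainly one of completeness, and its effect on precision is small.

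**Chance of a complete count**

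If survey return is unrelated to having had a problem, the chance that the survey picks up all of three true problems is 0.8³ = 51% (0.6³ = 22% at 60% return, 0.9³ = 73% at 90%).

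**Choice of denominator**

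At 30% use, three problems are 3/360 = 0.8% of users but 3/1200 = 0.25% of women sent a kit. Using only the second figure would dilute an outcome about device use.

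**The case against.** The strongest reply is that little depends on this. Safety carries no hypothesis, threshold or group comparison. It is one descriptive secondary analysis in a study described as minimal risk, and the survey goes to returners and non-returners alike with a paid incentive. That stands, and it keeps the point minor.

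Three stronger readings are tempting, and the documents do not support them.

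- A reader might infer that the plan excludes problems reported outside the survey. It is silent and states no exclusion, and the sentence in Secondary Analyses is not itself limited to the survey. The navigator forms and scripts are in appendices not shown, so they may already have a place to note problems.
- A reader might infer that women are told to call the clinic or the study team about device problems. The two risk sections say that contact information is given, without naming whose. Clinic and navigator details are named only in connection with results. The clinic or navigator is the natural reading for device problems too, but it remains a reading.
- A reader might take every woman without a survey as lost safety data. Most of the 240 would be non-users on the assumed range. Some women may have tried the device without returning it, but their number is unknown.

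It is also fair to say that unsolicited reports are uneven. A woman who returns her kit promptly and tests negative has no planned navigator call, and silence from someone never asked is not a confirmed zero. Adding these reports therefore does not bring the bound down to the all-users column. This limits how the second source may be used; it does not justify leaving known problems out.

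**Conclusion.** The point holds as a minor one. Followed as written, the rule in Table 1 and Measures can leave out device problems that clinic staff already know of, in women who do not return the survey. The direction is certain for the count of known problems, which can only be too low. It is not certain for the rate among responders, since women with a problem may be more or less likely to answer.

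The group without a survey is about 240 of 1200 women sent a kit, resting on the plan's 80% return. About 48 to 96 of them would be users, resting on my assumed 20% to 40% use and on equal survey return in users and non-users. How many of these would report a problem by another route cannot be estimated from the documents. Power and the primary comparison are not affected.

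**What to change.** In Table 1 and Measures, add a second safety source: any device problem or negative outcome reported to navigators, clinics or the project team, logged by participant ID and sent to the team through the existing ID-only data flow. Use the navigators' existing project forms where possible.

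In Secondary Analyses, state that:

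- counts are reported by source, with each woman counted once in the total;
- two denominators are shown, women who returned a kit (known users) and all women sent a kit;
- the survey-only rate among responding users remains the rate estimate, because the other reports are not collected evenly.

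The cost is a small logging task, though it falls on clinics across 10 health systems and must continue in the Sustainability phase, when the project team has stepped back. Ascertainment will differ between sources, which is why they are reported separately. No extra visits or mailings are needed.

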Note. Some of the materials included as appendices with this submission will be further refined by the study team. Upon completion, final versions will be submitted for IRB review and approval in a future amendment. IRB approval will be obtained prior to the use of the final versions in the study.

Figure 1. Project Overview

Health Systems and Clinics

The P01 program will involve a total of 10 health systems in four states. A letter of support from each system has been included. Several of the health systems include multiple clinics. Similar to the other projects in this P01 program, all activities and participants will stem from these health systems/clinics (as described below).

Year 1 Preliminary Activities

During Year 1, we will conduct two necessary preliminary activities outside of the GRT portion of the study: training of patient navigators and provider education sessions.

Training of Patient Navigators

PN will be provided during the randomized trial to help women both: a) use/return their HPV self-test (if they do not initially return their device); and b) attend an in-clinic follow-up visit if their returned self-test is positive for high-risk HPV infection. Patient navigators (PNs) will perform the following activities during the trial: a) provide information about HPV, cervical cancer, and screening; b) address patients' concerns/barriers about HPV self-testing and attending a follow-up visit (if needed); c) help set goals and plans for achieving these outcomes; and d) provide social support. These activities are key components of behavior change technique³³ and were used in our past PN work.³⁴ The PNs will be health system/clinic staff that have agreed to serve as PNs for this project.

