We will next mail all identified potentially eligible women a standard reminder letter to get a clinic-based cervical cancer screening test (e.g., Pap test) (see Appendix). The letter will indicate that, according to EHR, they are due for a clinic-based cervical cancer screening test and encourage them to contact their clinic to schedule a test (contact information for the clinic will be provided). All letters will appear on clinic/health system letterhead and be signed by a clinic representative. Many health systems have utilized this type of reminder letter for cervical cancer screening,³⁶ so it can be considered "usual care." We think it is important that all potentially eligible women receive this letter that encourages clinic-based cervical cancer screening test before any HPV self-tests are sent. The clinics will mail all of the reminder letters to women. Members of the project team will not have access to any identifying information (including contact information) of the patients. All communication between the project team and clinics about patients will involve only ID numbers.

We will allow about 4-5 months for women who are sent a reminder letter to receive a clinic-based cervical cancer screening test. At the end of the this time period, we will work with the clinics/health systems and use EHR to

identify women who received a clinic-based cervical cancer screening test since the reminder letters were sent. Any woman who has received a test will not continue in the project, as they are no longer unscreened/underscreened. Based on the mean effect size of past studies of mailed cervical cancer screening reminder letters, we anticipate that only about 5% of women who are sent a reminder letter will receive a clinic-based test during the 4-5 month period.³⁶

Randomization

Health systems will be randomized to one of two treatment groups (Group 1 or Group 2) for the cervical cancer prevention program (Figure 1). A 1:1 allocation scheme stratified by state will be used (i.e., five systems per treatment group). Health system will be the unit of randomization. All clinics in a health system will be in the same treatment group.

Year 2 Randomized Trial Activities

[figure not shown]
Group 1: Early Intervention

Group 1 clinics/health systems will receive Early Intervention during Year 1, including HPV self-test devices sent to women (patient-level component) and PN (system-level component). Figure 2 provides an overview of these components.

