The project's total sample size will be 1800 women across Years 2-5 (900 women from Group 1 clinics/health systems and 900 from Group 2 clinics/health systems). These sample sizes are feasible given the expected sampling frame size (see Table 1) and will give us at least 90% power for the below analyses.⁴³ The power calculation assumed a two-sided alpha=0.05, an intraclass correlation coefficient<0.017 (based on our pilot study), and the below outcome occurrences.

Primary Analyses

Primary analyses will examine the proportion of women from Year 2 screened, as defined above, and use an intent-to-treat approach. To compare treatment groups (Group 1 vs. Group 2), we will use generalized linear mixed models (GLMMs) to account for the correlation between women from the same clinic,⁴⁴ though we expect cluster effects to be low (i.e., intraclass correlation coefficient<0.017 based on our pilot study). Since our outcome is binary, we will use a logit link to estimate odds ratios for the GLMMs. We expect that 30% of women from Group 1 clinics/health systems and 10% of women in Group 2 clinics/health systems will be categorized as screened. The primary model will be unadjusted, but we will conduct sensitivity analysis that include potential confounders due to imbalance from randomization ($p<0.10$ when comparing groups). Results will determine the effectiveness of the intervention in increasing cervical cancer screening compared to usual care.

Secondary Analyses

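### The primary GLMM models clinic but not health system, the randomised unit; it also omits state and names no degrees of freedom for 10 units, so the 5% level is not assured.

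*Combined protocol and SAP*

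**What the plan says.** - **Units.** Health Systems and Clinics: "The P01 program will involve a total of 10 health systems in four states", and "Several of the health systems include multiple clinics".
- **Allocation.** Randomization: "A 1:1 allocation scheme stratified by state will be used (i.e., five systems per treatment group"), and "Health system will be the unit of randomization. All clinics in a health system will be in the same treatment group".
- **Primary model.** Aim 1, Primary Analyses: "we will use generalized linear mixed models (GLMMs) to account for the correlation between women from the same clinic", "though we expect cluster effects to be low (i.e., intraclass correlation coefficient<0.017 based on our pilot study"). The link is logit and the population is the Year 2 women by intention to treat.
- **Covariates.** The same section: "The primary model will be unadjusted, but we will conduct sensitivity analysis that include potential confounders due to imbalance from randomization", with covariates chosen by p<0.10 between groups.
- **Level.** Sample Size: "The power calculation assumed a two-sided alpha=0.05".

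No section adds a health-system effect or a state effect to the primary model. None names a test statistic, denominator degrees of freedom, a small-sample method or a permutation test.

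**The concern.** The arm effect is a contrast between health systems, five against five. Clinics of one system always share an arm, so anything that makes one system differ from another enters that contrast in full. A model with clinic as its only cluster treats the clinics of a system as independent replicates. It therefore leaves that variance out of the error and credits the comparison with more units than were randomised. A z reference, which a GLMM analysis may use if nothing is specified, adds to the problem when there are only 10 units.

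Leaving out state acts the other way. Stratified allocation balances states between arms, but without a state term the variance between states stays in the error and makes the test conservative. The documents do not show which effect is larger.

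This is the trial's primary test. If systems within a state differ, the p-value and the odds-ratio interval overstate certainty.

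**Working it through.** **Inputs from the documents.** 600 women per arm in Year 2; 5 systems per arm, so 120 women per system if equal; 30% versus 10% screened; two-sided alpha 0.05; ICC below 0.017 (upper bound used); stated power at least 90%.

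**Assumptions.** Clinics per system (2, 3, 5, or a mix of one and three), the shares of the ICC at system and state level, the reference distribution, and states of 2, 2, 2 and 4 systems. That is the only split of 10 systems over four states that allows exact 1:1 in each.

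**1. The plan's power.** With system as the cluster, the design effect is 1 + 119 × 0.017 = 3.023 and the effective n per arm is 600/3.023 = 198.5. The standard error of the difference is √(0.30/198.5) = 0.0389, and 0.20/0.0389 = 5.14. Power is 99.9% with z, 99.4% with t on 8 df and 98.1% on 5 df. The stated 90% holds, so the fault is not one of power.

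**2. The reference distribution alone.** If a statistic truly follows t on 8 df, a cut-off of 1.96 has two-sided error 8.6%; on 5 df, 10.7%.

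**3. Type I error of the clinic-only logit GLMM.** Simulated with 10% screened in both arms, 10 systems of 120 women, 2,000 replicates per scenario (Monte Carlo error about 0.5 point at 5%, 0.9 at 20%). Ranges run over the clinic layouts at ICC 0.017. Columns give the part of the system variance that lies between states.

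| ICC at system level | Reference | None | Half | All |
|---|---|---|---|---|
| None | z | 6.0-7.8% | – | – |
| Half | z | 10.7-13.5% | 8.4-8.7% | 4.5-7.2% |
| All | z | 15.7-19.9% | 8.3-12.9% | 2.7-3.3% |
| None | t, clinic df | 5.1-6.3% | – | – |
| Half | t, clinic df | 8.6-12.4% | 6.3-7.5% | 3.0-5.6% |
| All | t, clinic df | 13.4-19.0% | 6.1-12.0% | 1.8-2.4% |

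A separate simulation that compared clinic means, with no state variance and z, gave 13.8%, 16.6% and 19.9% for 2, 3 and 5 clinics with all of the ICC at system level. With half, it gave 9.4%, 11.4% and 12.7%.

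With one clinic per system, where clinic and system coincide, the GLMM gives 10.3 / 7.0 / 3.0% with z and 6.4 / 4.3 / 1.7% with t on 8 df. At ICC 0.005, all at system level, z gives 8.9-10.6 / 5.5-6.7 / 3.7-4.1%.

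**4. Interval width at 30% versus 10%.** Three clinics of 40 per system, ICC 0.017, no state variance.

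- Design effects: clinic only, 1 + 39 × 0.017 = 1.663; half at system level, 1.663 + 80 × 0.0085 = 2.343; all, 3.023.
- Odds ratio: (0.30/0.70)/(0.10/0.90) = 3.86.
- SE of the log odds ratio: √[DE × (1/126 + 1/54)] = 0.210, 0.249 and 0.283, where 126 = 600 × 0.3 × 0.7 and 54 = 600 × 0.1 × 0.9.
- Clinic only with z (1.96): 2.56-5.82.
- 8 df (2.306): 2.17-6.85 (half) or 2.01-7.40 (all).
- 5 df (2.571): 2.03-7.31 (half) or 1.86-7.98 (all).

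**5. Smallest significant Group 1 rate against 10%, same layout.** Clinic only with z: 14.8%. On 8 df: 17.0% (half) or 18.0-18.2% (all). On 5 df: 17.9-18.0% or 19.1-19.3%. Rates from about 15% up to 17-19% would thus be significant under the clinic-only model with z but not at system level.

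**The case against.** The strongest reply is that the direction is unknown. At ICC 0.017 with z, the figures run from 2.7% to 19.9% on quantities the documents do not give, and with no variance between systems the clinic-only model is nearly valid. That stands. It supports a level that is not assured; it does not demonstrate inflation.

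Second, omitting state makes the test conservative, so it is not itself a route to false positives. That also stands. State matters here because the error can be wrong in either direction, and because the stratification determines the degrees of freedom.

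Third, the plan does not say z. True; the z figures are conditional on that choice. But t on clinic-level degrees of freedom still gives 13.4-19.0% in the worst case.

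Fourth, 0.017 is an upper bound. At ICC 0.005 (three clinics, all at system level, no state variance) the cut-offs are 14.0% for clinic only with z, 15.6% on 8 df and 16.3% on 5 df, a narrower window. The window shrinks but does not close.

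Fifth, the planned effect survives, since even the widest interval in the working excludes 1. Agreed, but a primary analysis has to be valid for whatever effect is observed.

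Finally, the recommended nested model is itself conservative. That is correct, and it is part of the cost set out with the change.

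**Conclusion.** The concern holds. This is more than missing detail: the plan states a primary model whose only cluster is not the unit that was randomised, and its sensitivity analysis adds covariates without adding the missing level.

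If systems within a state differ, the true level may be well above 5%: about 14% to 20% with z over the two simulations in the extreme case (ICC 0.017, several clinics per system, all of the ICC between systems, no state differences). If the differences lie mainly between states, it is near or below 5%. If systems do not vary beyond their clinics, it is about 5-8%, depending on the reference distribution. Nothing in the documents excludes any of these cases.

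The practical risk is a false claim on a modest effect, with Group 1 at roughly 15-19% against 10%, and an odds-ratio interval that is too narrow. The expected result would not be overturned. The model should be corrected before the primary analysis.

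**What to change.** Specify the primary GLMM with a random intercept for health system, and clinic nested within it where a system has several. Name a restricted (REML-type) pseudo-likelihood method. Include state as fixed effects, because allocation is stratified by state, and test the arm effect on 10 − 1 − 3 − 1 = 5 between-system df. Omitting state and using 8 df is also valid, but conservative if states differ. Choose one before the analysis.

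Simulated type I error at ICC 0.017:

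- nested model with state, 5 df: 0.3-3.7%;
- nested model without state, 8 df: 0.2-4.8%;
- nested model with state by plain maximum likelihood, 5 df: up to 7.7%, so it should not be used.

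Add two checks. A linear model of the 10 system proportions with state effects on 5 df has simulated error 3.9-6.3%. A permutation test within states has 2.1-3.7%. With states of 2, 2, 2 and 4, the permutation test has 2 × 2 × 2 × 6 = 48 allocations and a smallest two-sided p of 2/48 = 0.042, so it suits a check better than the primary test.

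The cost is wording; no new data or patients are needed. The price is a wider interval. At 30% versus 10%, with all of ICC 0.017 at system level, power is about 99% on 8 df, 98% on 5 df and 93% for the permutation check, all above the stated 90%. At 20% versus 10%, state effects on 5 df give 62% against 71% on 8 df if states do not differ. If half of the system variance is between states, they give 77% against 72%.
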